12.5.7 ADDITIONAL EXPLORATORY ANALYSES

The following additional effectiveness analyses will be provided at the time of regulatory submission:

- Number of meibomian glands yielding clear liquid secretions
- Number of meibomian glands secreting any liquid (clear or cloudy)
- Use of dry eye lubricants, collected through counting unused vials of Refresh Plus

The meibomian gland-related measurements will be analyzed in the same manner as the per-eye secondary endpoints.

Lubricant use will be summarized by Treatment group at each follow-up visit.

12.5.8 Modeling of Extended Follow-up Results

After the initial 1 month primary analysis, subjects will be followed up to 12 months to evaluate durability of the treatment effect. After the 6 month visit, subjects in the Warm Compress group will cross over into the TearCare arm. Treatment duration will be evaluated primarily via comparisons of treatment versus control change in TBUT at each of the 3- and 6-month time points separately as described in 12.5.6.

[figure not shown]
After 6- and 12-month follow-up is complete the longitudinal study data will be reanalyzed, again using LME modeling methods. These models will allow us to evaluate the following:

- Maintenance of the Treatment effect using the full longitudinal data on each subject,
- A more detailed evaluation of the baseline effects, if any.

At the 12 month follow-up the Warm Compress subjects will have received TearCare treatment at 6 months, thus we will lose a comparison to randomized control subjects at this point. However for those subjects who receive TearCare at 6 months we will be able to carry out a before- versus after- TearCare comparison, which may provide useful supplementary information.

12.5.9 SAFETY ANALYSIS

All adverse events will be reported by treatment group and AE category. Any serious adverse events will be completely described in the study report.

12.7 SAMPLE SIZE CALCULATION

A total of 200 subjects, 100 in the TearCare group and 100 in the Warm Compress group, will be enrolled and randomized in the study. Sample size was calculated to provide more than 90% power for the TBUT and OSDI effectiveness endpoints and sufficient precision around the adverse event estimates. The sample size also takes into account an estimated 10% dropout rate. Details of the sample size calculation can be found in Appendix C.

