12.2 Analysis Populations

The per-protocol analysis population includes all subjects who have at least one post-treatment visit and have no major protocol deviations, including specifically no use of dry-eye medications (Xiidra, Restasis). The primary and secondary endpoint analyses will be carried out on the per-protocol population. The primary analysis population will be per-protocol.

The intent-to-treat (ITT) analysis population includes all subjects who are randomized to either arm, regardless of treatment received. The primary and secondary endpoint analyses will also be carried out on the ITT population as well.

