23.2 SAMPLE SIZE CALCULATIONS

23.2.1 TEAR BREAKUP TIME

The primary Tear Breakup Time (TBUT) endpoint is measured on a per-eye basis. In order to account for the correlation between eyes the sample size is calculated in two steps. The first step is to carry out a standard sample size calculation for the number of eyes based on a two-sample t-test with unequal variances. This test is appropriate for a sample of independent eyes from the two groups, that is, a study in which only one eye per subject is enrolled. The second step is to allow for two eyes per subject by adjusting the independent sample size to account for the correlation between eyes.⁵⁷ This is done by multiplying by a "design effect" (DEFF) that can be calculated from the pilot study data (provided in Section 5.2.2). Finally we allow for some loss to follow up and then divide by 2 (eyes per subject) to arrive at a final enrolled sample size in terms of number of subjects.

[figure not shown]
This sample size calculation does not account for the adjustment for baseline TBUT in the analysis model. That adjustment should only serve to increase the power of the test, so this simpler calculation is conservative in that sense.

For the sample size calculation, a positive treatment effect for the warm compress control was assumed, reducing the TBUT time per eye by 4 seconds, with a standard deviation of 2. This is somewhat conservative based on the pilot study data (this is on the upper end of what we expect to see for the Warm Compress group).

For the TearCare device a treatment effect of 6 seconds, with standard deviation 3 was assumed. This is also somewhat conservative, as it is on the lower end of what we expect to see in the TearCare group based on the pilot study data.

[figure not shown]

Finally, we will assume that 10% of the enrolled subjects will be lost to follow-up. Based on these assumptions, Table 4 shows sample sizes for powers of 80%, 90%, and 95%.

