23.2.2 OSDI

The most important secondary effectiveness endpoint, OSDI, measures subject-reported symptoms. This endpoint is measured on a per-subject basis, so no adjustment for correlation is necessary. For this endpoint a minimum clinically important difference ranges from 7.0 to 9.9 units. ⁵⁹ Based on data from the TearCare pilot study, we conservatively assumed a 10-point OSDI improvement in the Warm Compress group and an 18.5 point improvement in the TearCare group, and a standard deviation of 18

CONFIDENTIAL Sight Sciences

units. Using these assumptions, the following Table 5 shows the power for a two-sample t-test with unequal variances for a range of sample sizes.

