23.2.4 SAMPLE SIZE SUMMARY

Based on the calculations outlined above, an overall sample of 200 individuals, with 100 in the TearCare group, will provide more than 90% power for the TBUT and OSDI effectiveness endpoints and sufficient precision around the adverse event estimates.

24 Appendix D - Declaration of Helsinki

I. PREAMBLE

 The World Medical Association (WMA) has developed the Declaration of Helsinki as a statement of ethical principles for medical research involving human subjects, including research on identifiable human material and data.

The Declaration is intended to be read as a whole and each of its constituent paragraphs should be applied with consideration of all other relevant paragraphs.

 Consistent with the mandate of the WMA, the Declaration is addressed primarily to physicians. The WMA encourages others who are involved in medical research involving human subjects to adopt these principles.

II. GENERAL PRINCIPLES

- The Declaration of Geneva of the WMA binds the physician with the words, "The health of my patient will be my first consideration," and the International Code of Medical Ethics declares that, "A physician shall act in the patient's best interest when providing medical care."
- It is the duty of the physician to promote and safeguard the health, well-being and rights of patients, including those who are involved in medical research. The physician's knowledge and conscience are dedicated to the fulfilment of this duty.
- Medical progress is based on research that ultimately must include studies involving human subjects.
- 4. The primary purpose of medical research involving human subjects is to understand the causes, development and effects of diseases and improve preventive, diagnostic and therapeutic interventions (methods, procedures and treatments). Even the best proven interventions must be evaluated continually through research for their safety, effectiveness, efficiency, accessibility and quality.
- 5. Medical research is subject to ethical standards that promote and ensure respect for all human subjects and protect their health and rights.

- While the primary purpose of medical research is to generate new knowledge, this goal can never take precedence over the rights and interests of individual research subjects.

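### Section 12.7 claims more than 90% power for OSDI with 10% dropout allowed for; at an assumed two-sided 5% level the plan's inputs give 88.3% with 90 per arm

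*Combined protocol and SAP*

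**What the plan says.** Section 12.7 sets the trial at 200 randomized subjects, 100 per arm. It says "Sample size was calculated to provide more than 90% power for the TBUT and OSDI effectiveness endpoints" and then "The sample size also takes into account an estimated 10% dropout rate". The dropout sentence is not limited to one endpoint, so a reader will take the power figure as holding for both TBUT and OSDI after 10% loss. The section refers to Appendix C for details.

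In Appendix C, section 23.2.2 gives the OSDI inputs: "we conservatively assumed a 10-point OSDI improvement in the Warm Compress group and an 18.5 point improvement in the TearCare group". The SD is given as 18, the test is a two-sample t-test with unequal variances, and there is one observation per subject, so no between-eye adjustment. Its visible text mentions no dropout. The loss allowance stands in the TBUT calculation, section 23.2.1: "Finally, we will assume that 10% of the enrolled subjects will be lost to follow-up". The summary in section 23.2.4 says that 200 individuals "will provide more than 90% power for the TBUT and OSDI effectiveness endpoints" and does not mention dropout.

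On the population, section 12.2 states: "The primary and secondary endpoint analyses will be carried out on the per-protocol population". The same analyses are also run on the intent-to-treat population, but per-protocol is named as primary.

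**The concern.** The 10% loss appears to have been built into the TBUT sample size and not into the OSDI one, with section 12.7 then attaching it to both. If so, the OSDI figure describes 100 evaluable subjects per arm, while the sentence beside it promises that figure after losing 10 of them.

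Section 6.1 names OSDI as the key secondary endpoint, and it is the only symptom endpoint for which power is calculated. The proposed indication (section 4.2) covers signs and symptoms, while the primary endpoint, TBUT, measures signs. The symptom part of the claim therefore leans on OSDI. The margin must also absorb more than missed 1-month visits: section 12.2 removes subjects with major protocol deviations, including use of Xiidra or Restasis, from the population on which the secondary endpoints are primarily analyzed.

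**Working it through.** **Inputs**
- Difference: 18.5 − 10 = 8.5 points (23.2.2).
- SD: 18. One value is given, and I apply it to both arms (23.2.2).
- Test: two-sample t-test, per subject (23.2.2). With equal SDs and equal n, the unequal-variance version has the same standard error.
- Subjects: 100 per arm randomized (12.7). After 10% loss, 100 × 0.90 = 90 per arm.
- Alpha: not in the available text. Assumed two-sided 5% (one-sided 2.5% gives the same results); one-sided 5% is shown as the alternative.

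**Formula.** The standard error is SE = 18 × √(2/n). The noncentrality is 8.5/SE on 2n − 2 degrees of freedom. Power is the probability that the noncentral t statistic falls beyond the critical value.

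**Step 1: reproduce the plan's figure.** With n = 100, SE = 18 × √0.02 = 2.546, noncentrality = 8.5/2.546 = 3.339, and power = 91.4%. The claim of more than 90% is reproduced with every randomized subject evaluable.

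**Step 2: apply the stated dropout.** With n = 90, SE = 18 × √(2/90) = 2.683, noncentrality = 8.5/2.683 = 3.168, and power = 88.3%. Simulating the unequal-variance test (200,000 trials) gave 88.4%, and the normal approximation gives 88.6%. None reaches 90%.

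**Step 3: how much loss is covered.**

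| Evaluable per arm | Loss from 100 | Power, two-sided 5% |
|---|---|---|
| 100 | 0% | 91.4% |
| 96 | 4% | 90.2% |
| 95 | 5% | 89.9% |
| 90 | 10% | 88.3% |

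The smallest n per arm with at least 90% power is 96, so no more than 4 subjects per arm may be lost from the 1-month analysis.

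**Step 4: sensitivity to alpha.** At one-sided 5%, power at 90 per arm is 93.5%, and 78 per arm would be enough for 90%. There is then no shortfall.

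**Step 5: sensitivity to the inputs.** At 90 per arm and two-sided 5%, power reaches 90% if the SD is about 17.5 (difference 8.5) or the difference is about 8.75 (SD 18).

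**Step 6: baseline adjustment.** Take 18 as the SD of the change score, with equal SDs at baseline and 1 month and correlation r between them. Analysis of covariance then has residual SD 18 × √((1 + r)/2). At 90 per arm (2n − 3 degrees of freedom, two-sided 5%):

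| Assumed r | Residual SD | Power |
|---|---|---|
| 0.5 | 15.59 | 95.3% |
| 0.7 | 16.60 | 92.7% |
| 0.8 | 17.08 | 91.3% |

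Power stays above 90% up to r of about 0.88.

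**Step 7: TBUT.** With a difference of 2 s, SDs of 3 and 2, and 90 subjects (180 eyes) per arm, power is above 99.9% for any between-eye correlation from 0 to 1. The problem is confined to OSDI.

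**The case against.** The strongest reply is that the deciding text cannot be seen. The contents list a section 12.6 on hypotheses, but its body is not available, so the alpha and sidedness are unknown; at one-sided 5% both sentences of section 12.7 are true. Table 5, which shows OSDI power for a range of sample sizes, is also missing and may already distinguish evaluable from randomized subjects. Other sections say that section 12.5.5 describes a hierarchical procedure, yet its visible text only lists endpoints, so method text is absent there too. If that text adjusts OSDI for baseline, power after dropout probably exceeds 90%.

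There are also reasons to expect less than 10% loss at 1 month. The 10% carries no time point and follow-up runs for 12 months (9.2); all 24 subjects in the 2017 pilot completed 6 months (5.2.2); and subjects who withdraw before treatment may be replaced (9.9). Section 23.2.4, read alone, is correct at 100 per arm. Finally, 1.7 points is small beside the uncertainty in the SD, and section 23.2.2 calls its assumed improvements conservative.

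Most of this stands as a limit on the finding. It makes the result conditional on alpha and shows that the trial is not seriously underpowered. It does not reconcile the two sentences under the conventional two-sided 5% level: section 12.7 presents the 10% as already allowed for, without limiting it to TBUT, and section 23.2.2 bases its power on an unadjusted t-test. The remark that baseline adjustment makes the calculation conservative is made in section 23.2.1, for TBUT only.

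**Conclusion.** The concern holds, conditional on a two-sided 5% (or one-sided 2.5%) test. The plan's inputs then do not give more than 90% OSDI power after the dropout that section 12.7 says is covered. If 10% are lost by 1 month, the chance of missing a true 8.5-point difference is 100 − 88.3 = 11.7%, rather than under 10%. The covered loss is about 4% against the 10% stated, and per-protocol exclusions must come out of the same margin.

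The conclusion rests on the assumed alpha, an SD of 18 in both arms, and an unadjusted comparison. It concerns one overstated figure for the key secondary endpoint; the primary endpoint and the sample size itself are not called into question. Confidence is medium, because section 12.6, Table 5 and the method text of section 12.5.5 are not available.

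**What to change.** In sections 12.7 and 23.2.4, give OSDI power as about 88% with 90 evaluable per arm, and 91% only with no dropout. State the alpha and sidedness behind the figure, and whether the sample sizes in Table 5 are randomized or evaluable subjects. If the test is one-sided 5%, say so and keep the present claim.

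If it is not already planned, analyze 1-month OSDI change with baseline OSDI as a covariate. Under the assumptions in step 6 this restores power above 90% at 90 per arm for correlations up to about 0.88.

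The cost is one figure restated in two places, a sentence on alpha and n, and at most one line for the OSDI model. Baseline OSDI is already collected (section 12.4). No extra subjects or visits are needed.

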12.8 INTERIM ANALYSIS

The primary analysis for this study will occur after the final subject reaches their 1 month follow-up. The results of this analysis will be used for regulatory submission. Further analyses after all subjects have reached their 6- and 12-month follow up will be used to investigate duration of the TearCare treatment effect as outlined above.

There will be no interim analyses.

12.9 DEVIATION FROM THE STATISTICAL PLAN

Any deviations from the statistical plan will be noted in the final report.

13 Monitoring Procedures

Sight Sciences or contract research organization (CRO) personnel will monitor the study in a manner consistent with FDA regulations, good clinical practices and the clinical research standards adopted by Sight Sciences. Study monitoring will involve the following elements:

 Site Qualification: Sight Sciences or CRO personnel will meet with investigators and clinical study staff prior to the initiation of the study in order to review the adequacy of the subject population, facilities, and equipment with respect to

CONFIDENTIAL Sight Sciences

- the needs of the study, and to familiarize the investigator with the study protocol.
- Site Initiation: Sight Sciences or CRO personnel will meet with the
 investigator(s) and clinical study staff when the site is ready to begin enrolling
 subjects in order to train them in how to properly select subjects, perform the
 study procedure, and record study data. This visit will include, but not be
 limited to a review of the following:
 - Detailed review of the protocol
 - Informed consent procedures
 - Randomization procedures
 - Instruction in how to use the TearCare System
 - Guidance in how to instruct subjects to use the warm compress at home and perform lid massage at home.
 - o Guidance in how to administer questionnaires to subjects
 - Procedures for maintaining masking of study personnel
 - Records and reports
- Interim Monitoring: Sight Sciences or CRO personnel will visit the clinical site
 routinely during the study to review charts and to perform source document
 verification, to ensure proper adherence to the study protocol, and to review
 regulatory documents. Interim monitoring visits and telephone consultation
 will occur as necessary during the course of the study to ensure the proper
 progress and documentation of the study findings.
- Study Closure: At the conclusion of the trial there will be a study closure visit during which several actions, including but not limited to the following, will be performed:
 - A final inspection of the study binder
 - Accountability and return of all devices and study materials to the sponsor
 - Discussion of record retention requirements with the investigator
 - Close-out notification to the IRB

14 DATA AND QUALITY MANAGEMENT

14.1 DATABASE MANAGEMENT

The study database will be designed using an electric data capture (EDC) system that is compliant with 21 CFR Part 11 and relevant guidance documents. The EDC will be developed and maintained by an independent, qualified data management firm.

The database will incorporate time-stamped audit trails, protection of human subjects, restricted access, and data security at the component level. Each database module,

including each individual eCRF, will be validated by conducting a series of standard tests that demonstrate usability and correctness of the database system. The database will be maintained on an ongoing basis and will be routinely backed up.

14.2 Subject Identification

The subjects will be identified by a five digit subject number composed of a one-digit study identification number, a two digit center identification number followed by a two digit sequential subject number. The subject identification will be assigned when informed consent is obtained. In this way, information contained in the study records will be kept as confidential as possible.

14.3 SUBJECT ACCOUNTABILITY

All subjects randomized and treated in this clinical investigation shall be monitored for the duration of the investigation. The clinical investigation shall be considered completed when all subjects that have been enrolled in the investigation have reached the final reporting period, excluding subjects who were withdrawn.

14.4 CONFIDENTIALITY

All medical records associated with the clinical investigation will be made available for review by Sight Sciences personnel, its contract research organization (CRO) and governmental/regulatory agencies involved. The results of the study may be published in the future for scientific and marketing purposes, but the identity (name) of each subject will not be revealed. All records will be stored in a secure area at the investigator's facility, the CRO, the data management firm and at Sight Sciences, Inc.

14.5 Source Data and Case Report Forms

Source data will be entered into a validated electronic system at each site by trained personnel in accordance with 21 CFR Part 11 requirements. Electronic entries will be 100% verified against corresponding source data at the sites and queried/corrected if needed to the extent possible. Medical site records serve as source data. In addition, data that are collected exclusively for the purpose of this study and not normally recorded in the subjects' medical records can be collected directly on the study worksheets provided by the sponsor and these study worksheets will serve as the source data.

Source data and study worksheets are to be maintained at the site in the subject records or in the medical records. All entries must be made in black or blue ink and changes must be made by strike-through only with date and initials or signature. All

source documents must be completed and signed by the authorized study personnel (e.g., study coordinator). No "white-out" is to be used on the source documents.

14.6 RETENTION PERIOD

Clinical sites are to retain any and all clinical trial material (documentation, photographs, etc.) for a period of two years from the date the marketing application is approved or two years after the investigation has been discontinued, or as directed by their institutional document retention requirements, whichever is the longest. After that time, the items must be returned to Sight Sciences for archiving. Unused medical devices are to be returned to the sponsor at the conclusion of the enrollment period.

15 PROTOCOL MODIFICATIONS AND DEVIATIONS

Protocol modifications may occur during the study. Each will be approved by the sponsor before implementation. Each will undergo Institutional Review Board (IRB) review and approval, as necessary.

Any deviations from this protocol intended to protect the life or physical well-being of a subject in an emergency are to be reported to Sight Sciences, Inc. as well as the IRB as soon as possible, and no later than 5 working days after the emergency occurred.

All protocol deviations will be documented using the Protocol Deviation form.

16 Device Failures and Malfunctions

All device failures or malfunctions should be recorded on the Device Deficiency Form and reported to Sight Sciences Customer Service [contact]).

17 ETHICAL CONSIDERATIONS

17.1 DECLARATION OF HELSINKI

This study shall be conducted in accordance with the Declaration of Helsinki (Appendix D).

17.2 Institutional Review Boards (IRB)

The study shall not begin at a site until approval has been obtained from the reviewing IRB. It is the Investigators' responsibility to obtain and maintain written approval of the study protocol and Informed Consent documents from the appropriate IRB. It is also the Investigators' responsibility to notify that body about any amendments to these documents and to follow the IRBs rules regarding the reporting of Adverse Events and Protocol Deviations related to the device and/or this study. Copies of all written approvals (identifying the study, the submitted and approved documents and the date reviewed) and the approved versions of the documents must be provided to Sight Sciences or its CRO.

The Investigators must file all correspondence with the IRB and forward copies of such correspondence to Sight Sciences.

